### C.2.2.2 Physical Activity and Weight Change

[figure not shown]
The Loyola-Ibadan Women's Study was initiated in 2000 to study the relationship between resting EE, AEE, and weight change in women from two contrasting social settings. In both metropolitan Chicago and rural Nigeria, women were enrolled in a longitudinal survey in which EE was measured at baseline using DLW, and weight and body composition were measured for 3 consecutive years (Table 3) [135]. Mean change in weight during the follow-up interval was 0.73 and 0.76 kg/y for the Nigerian and US women, respectively. Contrary to our hypothesis, no association was observed between activity EE at baseline and weight change in either site [136]. This result underscores our prior assertion that variation in AEE in free-living populations has not been convincingly shown to predict risk of obesity. Unfortunately, the sample size in this cohort is somewhat small, and we were limited to two sites.

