### C.2.3 Energy Expenditure, Body Composition and Markers of Chronic Disease

Our international collaborative study on hypertension has led to new insights on the relationship between EE, body composition and markers of chronic disease. In our initial survey, we noted a robust correlation between resting EE and BP. This observation was subsequently confirmed in a total sample of 1,567 individuals from independent samples in Nigeria, Jamaica and the US [121]. Resting EE is in turn strongly correlated with weight and BMI, since adiposity leads to an obligatory increase in muscle mass required for movement. Multivariate analysis subsequently confirmed, however, that the impact of resting EE on BP is independent of BMI and weight. In fact, no measures of adiposity remain significant after accounting for resting EE [121]. This observation suggests that at least one important mechanism by which obesity leads to increases in BP is through the correlated increase in muscle mass and resting EE. To further test this hypothesis, we recently completed a person-level meta-analysis of body composition and BP in 18,072 individuals from the populations we propose to include in this study [137]. Persons at the upper end of the BMI distribution have higher percent body fat, thus a unit increase in BMI leads to a smaller increase in lean mass than a comparable increase in BMI among the lean. Under the assumption that it is the increase in lean mass that influences BP, the slope of the BMI-BP relationship should be steeper among the lean. In meta-regression analysis of 13 population samples, we, in fact, observed a strong negative relationship between mean BMI and slope of the BMI-BP correlation for both SBP and DBP ( $p < 0.001$ ). This relationship had never been detected in studies of individual populations and demonstrates the value of studies that sample from a broad range of social contexts. Using this international comparative design, we have also detected novel

relationships between BMI and physiologic variables (e.g., leptin and angiotensinogen) as well as impacts of environmental factors on the heritability of common traits (e.g., height, BP, and BMI) [137]. We have also reported on the relationship between PA, measured using DLW, and blood pressure; in a small sample of Nigerian, Jamaican, and African-American adults, activity EE, independent of body size or composition, was found to be inversely associated with both SBP and DBP [48].

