## D.4 Measurement Procedures

### D.4.1 Activity Energy Expenditure

Total daily EE is comprised of three components: resting EE, AEE, and thermic effect of food. In this study, we are most interested in AEE and its relationship to weight change and insulin sensitivity. AEE will be measured by two methods: accelerometers and DLW. All participants in each site will wear an activity monitor for 6-9 days, while a subset will undergo the DLW procedure as well. Our previous experience with measurement of EE indicates that both resting EE and AEE are very stable traits, with within-person correlations of 0.9 and 0.8 at intervals of 1-2 years, respectively [135]. For those participants in the DLW

[figure not shown]
subset, resting EE will be measured by indirect calorimetry, and thermic effect of food will be estimated as 10% of total daily EE. All methods are described below.

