## D.7.2 Power Analysis

A statistical justification for the selected sample size is provided for each aim of the study according to the suggested analytical plan. Sample size estimation for each of these hypotheses will be obtained, and the maximum number required to test them with sufficient power (80% or higher) will be selected.

- 1) PA is negatively related to percent body fat and CV risk factors in the study populations at baseline.

It has been previously estimated (cf. Preliminary Studies) that the correlation between PA, measured with DLW, and body composition is between -0.6 and -0.5. A correlation of -0.33 or smaller (larger in absolute value) will be detectable with 83% power and maximum probability of type I error alpha = 5% using a one-sided Fisher's Z test and 75 subjects per site [194].

- 2) PA is negatively related to change in body fat composition.

- a) *Physical Activity Measured by Accelerometer:*

PA, measured by the accelerometer, is associated with changes in body composition. For design purposes we will use the approach described above in the analysis section (see D.7.1.2. method 3). That is, two AEE groups will be formed by using the median AEE as the cut point. A method developed by Frison and Pocock [195] will be applied to compare mean changes between groups in a longitudinal analysis, adjusting for baseline values. In this method the following assumptions are made: the correlation between any 2 weight determinations is ~ 0.60 and the minimum acceptable difference between the means is 0.25 standard deviations (i.e., effect size equals 0.25) [186]. There will be one baseline measure of weight and two follow-up measurements. An analysis of covariance approach will be used to adjust for baseline values. Thus, to detect the pre-specified minimum difference with 90% statistical power we will need to accrue 460 subjects per AEE group (230 in the Low and 230 in the High group). We will accrue a total of 500 individuals per site in anticipation of a conservative total attrition rate of ~ 20%.

- b) *Physical Activity Measured by Doubly Labeled Water:*

The correlation between AEE and change in body composition is anticipated to be weaker (i.e., smaller in absolute value) than that observed between AEE and body composition at baseline. Data from previous studies (cf. Section C: Preliminary Studies) suggest that the association between AEE and body composition remains constant across studies.

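### The Hypothesis 2 sample size (D.7.2, item 2a) rests on an unsourced weight correlation of about 0.60 that looks too low; the error is conservative, the target is never given in kg, and the stated 460 does not follow from the inputs

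*Combined protocol and SAP*

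**What the plan says.** D.7.2 item 2a splits participants at the median AEE and sizes the comparison as follows: "A method developed by Frison and Pocock [195] will be applied to compare mean changes between groups in a longitudinal analysis, adjusting for baseline values". The inputs are that "the correlation between any 2 weight determinations is ~ 0.60" and that "the minimum acceptable difference between the means is 0.25 standard deviations (i.e., effect size equals 0.25". On the design it says "There will be one baseline measure of weight and two follow-up measurements" and "An analysis of covariance approach will be used to adjust for baseline values". Power is 90%. Alpha and sidedness are not given for this item.

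The result is stated as 460 per AEE group, which the same sentence then breaks down as 230 low and 230 high. Each site enrols 500, with about 20% attrition expected.

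No section reports a test-retest correlation for weight or an SD of weight change. The nearest figures are these:

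- Table 3 gives weight SDs of 12.5 kg (Nigeria) and 21.6 kg (US) in the women's pilot cohort.
- C.2.2.2 reports for that cohort: "Mean change in weight during the follow-up interval was 0.73 and 0.76 kg/y for the Nigerian and US women, respectively".
- D.4.1 states that "both resting EE and AEE are very stable traits, with within-person correlations of 0.9 and 0.8 at intervals of 1-2 years".
- C.2.3 states: "Resting EE is in turn strongly correlated with weight and BMI".

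**The concern.** The correlation between repeated weights largely determines how precisely weight change can be compared between AEE groups. A value of 0.60 would mean that adult weight tracks over one or two years less well than resting EE or AEE in the same research programme, although resting EE is itself closely tied to weight.

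If 0.60 is too low, the plan misdescribes what the weight analysis can detect. That matters because B.9 says that either the presence or the absence of an association will have a clear interpretation. For the reader to judge a null result against the design, the design must say what size of difference it was built to detect, in a unit with meaning. Item 2a gives only 0.25 SD, without saying which SD.

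**Working it through.** **1. The plan's own figure.** The Frison-Pocock ANCOVA formula is n per group = 2(z_α + z_β)² V / d², with V = (1 + (r − 1)ρ)/r − ρ². Here r = 2 follow-ups, ρ = 0.60 and d = 0.25.

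- V = 1.60/2 − 0.36 = 0.44.
- Two-sided 5%, 90% power: 2 × 3.2415² × 0.44 / 0.0625 = 148 per group, 296 in total.
- One-sided 5%: 121 per group, 242 in total.
- To reach 230 per group (two-sided), V would have to be 230 × 0.0625 / (2 × 3.2415²) = 0.684. The maximum of (1 + ρ)/2 − ρ² is 0.5625, at ρ = 0.25, so no correlation gives 230. One-sided, V would have to be 0.839, which is also out of reach.
- Analysing follow-up weights alone or change scores, or using one follow-up, does not give 230 at 90% power, with or without 20% inflation. The only near match is 229, from 95% power plus inflation, which contradicts the text.
- Attrition: 500 × 0.80 = 400 completers, below 460. Retaining 460 would need 460/0.80 = 575.
- With the stated inputs, 200 completers per group give 96% or more power for 0.25 SD.

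**2. What 0.60 implies.** SD of change = SD × √(2(1 − ρ)), taking equal SDs at both times.

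- Nigeria: 12.5 × √0.80 = 11.2 kg.
- US: 21.6 × √0.80 = 19.3 kg.
- If change were roughly normal around the reported annual means, about 37% of the Nigerian women and about 60% of the US women would gain or lose more than 10 kg in a year.

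**3. The target in kg.** If the 0.25 refers to the SD of a single weight, it is 0.25 × 12.5 = 3.1 kg and 0.25 × 21.6 = 5.4 kg. The two-year mean gains in that cohort are 2 × 0.73 = 1.46 kg and 2 × 0.76 = 1.52 kg. The ratios are 2.1 and 3.6.

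**4. Sensitivity to the correlation.** Detectable difference = 3.2415 × √(2V/200) SDs, for ANCOVA with two follow-ups, 200 completers per group, 90% power and two-sided 5%.

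| ρ | V | n per group for 0.25 SD | Detectable (SD) | kg, Nigeria / US | Times smaller than at 0.60 |
|---|---|---|---|---|---|
| 0.60 | 0.4400 | 148 | 0.215 | 2.69 / 4.64 | 1.0 |
| 0.80 | 0.2600 | 88 | 0.165 | 2.07 / 3.57 | 1.3 |
| 0.90 | 0.1400 | 48 | 0.121 | 1.52 / 2.62 | 1.8 |
| 0.95 | 0.0725 | 25 | 0.087 | 1.09 / 1.89 | 2.5 |
| 0.97 | 0.0441 | 15 | 0.068 | 0.85 / 1.47 | 3.2 |

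The values above 0.60 are assumptions. The documents report 0.8 and 0.9 for AEE and resting EE, not for weight.

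**5. Method matters too.** Item 2a also points to step 3 of D.7.1.2, individual slopes over 0, 12 and 24 months. With three equally spaced weights, that slope is the 24-month change divided by 24. The variance factor is then 2(1 − ρ), and the detectable difference at 0.60 is 3.2415 × √(2 × 0.80/200) = 0.290 SD, not 0.215. The ANCOVA figure refers to the baseline-adjusted average of the 12- and 24-month weights, the slope figure to change at 24 months. The two should not be mixed.

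**The case against.** The strongest defence is that the error is on the safe side. If weight tracks better than 0.60, the study detects smaller differences than planned. The median split is used only for design; the final analysis in D.7.1.2 is a mixed model with continuous AEE, and what a null result excludes will be read from the confidence interval obtained. All of this stands, and it limits the consequence to a misdescribed design.

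It is also fair that the case against 0.60 is indirect. A mean gain of 0.75 kg a year does not bound the SD of change, and a correlation between resting EE and weight does not fix weight's own test-retest correlation. The kg figures come from women at two of five sites, whereas the study enrols both sexes equally. These limits stand. They leave 0.60 unsourced and hard to believe, but not disproved.

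A reader might infer three stronger things that the documents do not support:

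- **That detectability is misstated by a fixed factor of two to four.** The factor depends on a weight correlation that the documents do not give. Under the plan's ANCOVA it is 1.3 at 0.80 and 1.8 at 0.90, and it reaches 2 only at about 0.92.
- **That the low correlation explains the 460.** It does not: at 0.60 the formula already gives 296.
- **That the sponsor passed over its own data.** The documents do not say where 0.60 came from.

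**Conclusion.** The concern holds as one about an unsupported and probably pessimistic input, a target with no stated unit, and a sample size that does not follow from the inputs given. It is not a finding of insufficient power.

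Two parts differ in strength. The 460 is a defect on the face of the text: it is not reproducible, it is described both as a per-group number and as a total, and it exceeds the 400 expected completers. That conclusion assumes 5% alpha but holds one- or two-sided. The size of the correlation's effect is conditional: detectable differences 1.8 to 3.2 times smaller than at 0.60 if the true value lies between 0.90 and 0.97. In kg, that is 1.52 down to 0.85 (Nigeria SD) and 2.62 down to 1.47 (US SD), against 2.69 and 4.64 at 0.60. These figures assume two-sided 5%, 200 completers per group, equal SDs over time, and that 0.25 SD means the SD of a single weight.

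**What to change.** In D.7.2 item 2a:

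- Replace 0.60 with the 12- and 24-month weight correlations, or the SD of weight change, from the sponsor's three-year women's cohort. State that it covers women at two sites, and say what is assumed for men and the other sites.
- Recompute with one named method (ANCOVA on the follow-up weights, or slopes), one alpha and one sidedness. Say which SD the effect size refers to.
- Correct the 460, so that the per-group number, the total and the number after 20% attrition agree.
- State the detectable 24-month difference in kg, per site and pooled.

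The cost is one descriptive run on data the sponsor already holds and a rewritten paragraph. Enrolment need not change: even at 0.60 the stated inputs need 296 completers (two-sided 5%), and 400 are expected per site.

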## B.9 Summary

Although the “obesity epidemic” has received enormous attention in recent years, the mechanisms through which the energy budget is being perturbed are still not well understood. In particular, the role of declining AEE as a causal mechanism in population-wide increases in relative weight deserves much greater attention. Despite widespread perception that variation in normal activity levels (as opposed to voluntary increases in high-intensity activity, as typical of trials) is correlated with change in weight, the data do not support this conclusion. Research in this vital area has been handicapped by lack of access to precise objective methods of measurement. A new generation of epidemiologic research will be required before we can base causal inferences or public health recommendations on something more than assumptions. As with other chronic CVD, international comparisons could be particularly informative.

The test of our study hypothesis will be “two-sided”. That is to say, the presence or absence of an association can be given a clear interpretation. Of course, given the body of evidence that increased AEE has health advantages, absence of an association would not be taken to suggest that AEE is of no value. Rather, the correct interpretation would be that declining AEE is unlikely to be the driving force behind the rise in obesity, nor will modest increases in AEE be adequate to reverse the trends.

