## D.8 Limitations

This study is based on the premise that objective measurement of EE will be required to fully understand the causes of the on-going secular trends in obesity. Given prior research on the role of specific sedentary activities, it is reasonable to test the hypothesis that AEE will vary across the social settings we have chosen to study. The value of our study will be in quantifying the overall magnitude of this difference and its within-site relationship. We recognize that it is possible that increases in energy intake—rather than expenditure—could be the determining, or even sole factor, in weight gain and diabetes risk; demonstrating the absence of a PA-obesity relationship will directly support this alternative hypothesis. We will capture data on EI from questionnaires as well, although we recognize its limitations.

On the other hand, the net positive energy balance required to cause gradual weight gain can be quite subtle (in the range of 20-40 kcal/d for adults). Given that this net excess is likely to be due to a combination of both decreased AEE and increased caloric intake, the contrast in population means for AEE could be hard to define. As in all such etiologic studies, therefore, we run the risk of a false negative due to low power. This result, however, would not be uninformative since it would be important to know that large mean shifts in AEE were not driving this epidemic. At the same time, a wide distribution of AEE levels can be anticipated among participants within each site, and we anticipate finding important relationships in the individual-level analyses. The entire success of the project, therefore, does not rest on the group comparisons.

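### Hypothesis 2 is sized on 0.25 SD of weight and never converted to kg, so the plan does not show what a null result could exclude, although B.9 gives a null a fixed meaning

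*Combined protocol and SAP*

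**What the plan says.** Section D.7.2, item 2a, forms the comparison groups within a site: "two AEE groups will be formed by using the median AEE as the cut point". The inputs are a target stated as "the minimum acceptable difference between the means is 0.25 standard deviations (i.e., effect size equals 0.25", an assumption that "the correlation between any 2 weight determinations is ~ 0.60", and this measurement schedule: "There will be one baseline measure of weight and two follow-up measurements". For the analysis, "An analysis of covariance approach will be used to adjust for baseline values". Power is 90%, with 230 in each half. Each site accrues 500, with about 20% attrition expected. No alpha or sidedness is given for this item.

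The document's own figures on weight are elsewhere. Table 3 gives SDs of body weight in the Loyola-Ibadan women. For the same cohort, C.2.2.2 reports: "Mean change in weight during the follow-up interval was 0.73 and 0.76 kg/y for the Nigerian and US women, respectively".

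On interpretation, B.9 says that "the presence or absence of an association can be given a clear interpretation". It adds that absence of an association would mean declining AEE is unlikely to be the main driver of obesity, and that modest increases in AEE would not reverse the trend. D.8 admits a risk of a false negative from low power, but in discussing contrasts between population means. It then looks to the individual-level analyses to find the important relationships.

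**The concern.** A standardised target hides its size. Body weight varies widely between people, while the change over two years is small, so a modest fraction of the SD of weight can be a large difference in weight gained. If the design target lies well above the gain the investigators expect, a non-significant Hypothesis 2 is compatible with AEE effects that matter.

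B.9 leaves no room for that outcome, and D.8 attaches its low-power caveat to the group comparisons rather than to this analysis. A further null is realistic: C.2.2.2 already reports one in a cohort it describes as rather small. At stake is whether a non-significant result is published as evidence against AEE or as inconclusive.

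**Working it through.** **Inputs**
- From D.7.2: d = 0.25 SD, ρ = 0.60, one baseline and two follow-up weights, ANCOVA. 500 per site less 20% leaves 400, or 200 per half. Pooled: 2,000 completers, 1,000 per half.
- From Table 3 (women only): weight SD 12.5 kg (Nigeria), 21.6 kg (US).
- From C.2.2.2: 0.73 and 0.76 kg/y, so 2 × 0.73 = 1.46 kg and 2 × 0.76 = 1.52 kg in 24 months.
- Assumed, because item 2a does not state it: two-sided alpha of 5%.

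**1. The plan's own figure.** The Frison-Pocock ANCOVA variance factor is V = (1+ρ)/2 − ρ² = 0.80 − 0.36 = 0.44. Then n per group = 2V(1.96 + 1.2816)²/0.25² = 148, or 148/0.8 = 185 allowing for attrition (121 before attrition if one-sided). The stated 230 is not reproduced at 90% power. The difference is on the safe side: 0.25 SD has about 98% power at 230 per group and 96% at 200. The sample is large enough for the stated target, so the question is the target.

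**2. The target in kg**
- Nigeria: 0.25 × 12.5 = 3.1 kg; 3.125/1.46 = 2.1 times the mean gain.
- US: 0.25 × 21.6 = 5.4 kg; 5.4/1.52 = 3.6 times the mean gain.
- If SD of change was meant, ρ = 0.60 gives SD × √(2 × 0.40) = 11.2 and 19.3 kg, so the target is 2.8 and 4.8 kg.

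**3. Power for a gap equal to the mean gain.** If the gap builds up linearly, it is half-size at month 12, so the average over the two follow-ups is (0.5 + 1)/2 = 0.75 of the 24-month gap. Power = Φ(0.75 × gap/SE − 1.96), with SE = SD × √(2 × 0.44/n).

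| n per half | SD (kg) | SE (kg) | 24-month gap (kg) | Power |
|---|---|---|---|---|
| 200 (site) | 12.5 | 0.829 | 1.46 | 26% |
| 200 (site) | 21.6 | 1.433 | 1.52 | 12% |
| 1,000 (pooled) | 12.5 | 0.371 | 1.46 | 84% |
| 1,000 (pooled) | 21.6 | 0.641 | 1.52 | 43% |

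With a one-sided 5% test (1.645 in place of 1.96) these become 37%, 20%, 90% and 55%. The pooled rows apply each SD in turn to all five sites, because no other weight SDs are given.

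**4. A larger gap.** If the low-AEE half gained everything and the high half nothing, the gap would be twice the mean gain, 2.92 or 3.04 kg. Power is then 75% and 36% per site, and over 99% and about 94% pooled.

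**5. Sensitivity to ρ.** The 24-month gap detectable with 90% power is (1.96 + 1.2816) × SE/0.75, with V recalculated for each ρ. The values 0.90 and 0.97 are assumptions.

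| ρ | Site, SD 12.5 | Site, SD 21.6 | Pooled, SD 12.5 | Pooled, SD 21.6 |
|---|---|---|---|---|
| 0.60 | 3.6 kg | 6.2 kg | 1.6 kg | 2.8 kg |
| 0.90 | 2.0 kg | 3.5 kg | 0.9 kg | 1.6 kg |
| 0.97 | 1.1 kg | 2.0 kg | 0.5 kg | 0.9 kg |

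**6. The planned final model.** With ρ = 0.60, optimal weighting of the two follow-ups for a linear gap gives a variance factor of 0.352/0.56 = 0.629. Using AEE as a continuous, normally distributed variable multiplies the variance by 2/π. The 90%-power gap between halves at one site is then 3.2416 × SD × √(2 × 0.629 × 0.637/200), about 2.6 kg and 4.4 kg. Dividing by √5 for the pooled sample gives about 1.1 and 2.0 kg.

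**The case against.** The strongest reply is that item 2a is a simplified design calculation. D.7.1.2 makes the final analysis a mixed model on continuous AEE, and the five sites can be pooled. This largely stands: step 6 shows a clear gain, and the pooled model reaches gaps near the expected gain even at ρ = 0.60. But the document gives no such calculation for weight. Its five-site figure in D.7.2 concerns a correlation with change in body composition for AEE measured by doubly labeled water.

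Two stronger readings are tempting, and the documents support neither.

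- A reader might infer that the target is unattainable because it exceeds the whole expected gain. Mean gain is not a ceiling on a difference between halves. One half can gain more than the mean while the other gains nothing or loses, and step 4 already brings the Nigerian gap close to 3.1 kg.
- A reader might take the imbalance in D.8, which "can be quite subtle (in the range of 20-40 kcal/d for adults", as the AEE effect the study must detect. D.8 describes a mean net surplus, probably from lower AEE and higher intake together. It is not a contrast between AEE halves. In Table 1 the AEE SDs run from 230 to 566 kcal/d, so under normality the halves would differ by about 1.6 SD, roughly 370 to 900 kcal/d. The document does not say what weight gap that should produce, so no kg target follows from the D.8 figure.

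Scope is also limited. The SDs are from women at two sites, while the study enrols both sexes at five. B.3 gives 1.4 kg/y for Jamaica, or 2.8 kg in 24 months. The target exceeds that only if the weight SD there is above 2.8/0.25 = 11.2 kg, and none is stated. Finally, B.9 limits its null reading to AEE as the main driver and to modest increases, and D.8 says longer studies are needed for causal inference. These soften the claim but set no condition on reading a null.

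**Conclusion.** The concern holds in a limited form. On the document's own inputs, the per-site target for Hypothesis 2 is 3.1 to 5.4 kg, about 2 to 3.6 times the mean 24-month gain in the cohort that supplies the SDs. For a gap equal to that gain, power is about 26% and 12% per site and 84% and 43% pooled.

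This does not show that the study is inadequate. The power figures rest on two SDs from women, ρ = 0.60, linear accrual, an assumed two-sided 5% test and a median split. A higher ρ or the continuous-AEE model would improve them, and the document gives no SD of weight change with which to settle the matter. What is shown is that the stated basis does not establish which AEE-related weight differences a null result could exclude, while B.9 assigns a null its meaning regardless and the caveat in D.8 does not cover this analysis.

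**What to change.** 1. In D.7.2, item 2a, state the target and the detectable 24-month weight difference in kg, per site and pooled, with alpha and sidedness. Base them on the SD of weight change, or the correlation between weights, from the existing three-year Loyola-Ibadan cohort.
2. In B.9 and D.8, say that a null Hypothesis 2 result supports the conclusion that declining AEE is unlikely to be the main driver only on one condition: the 95% confidence interval for the AEE-related 24-month weight difference, from the final mixed model and for a stated AEE contrast, must exclude a pre-stated kg value justified against the expected gain. Otherwise, report the result as inconclusive at 24 months.

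The cost is wording in three sections and a recalculation from data the investigators already hold. No participants or procedures are added. The downside is a narrower claim from a null result.

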## D. EXPERIMENTAL DESIGN AND METHODS

### D.1 Project Overview

#### D.1.1 Participant Recruitment and Baseline Exam

Population-based samples, ages 25-45, will be drawn from communities in 5 countries: Nigeria, Seychelles, South Africa, Jamaica and the US; 500 per site, 2500 total. Based on our overall experience with

longitudinal studies, we experienced 2% annual attrition in Nigeria and 10% in the US site, we anticipate no more than 20% attrition by the 24-month examination, resulting in a final 'N' of at least 400 per site (Table 5).

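### Hypothesis 2 sample size (D.7.2, item 2a): 460 is labelled per AEE group but split 230 + 230, and the stated inputs give 296 or 242 in total, not 460

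*Combined protocol and SAP*

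**What the plan says.** D.7.2 item 2a splits participants at the median AEE and sizes the comparison by the method of Frison and Pocock for 90% power. Its inputs are:

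- Correlation and effect: "the correlation between any 2 weight determinations is ~ 0.60 and the minimum acceptable difference between the means is 0.25 standard deviations".
- Measurements: "There will be one baseline measure of weight and two follow-up measurements".
- Adjustment: "An analysis of covariance approach will be used to adjust for baseline values".

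It concludes that "we will need to accrue 460 subjects per AEE group (230 in the Low and 230 in the High group"). The next sentence reads "We will accrue a total of 500 individuals per site in anticipation of a conservative total attrition rate of ~ 20" per cent. D.1.1 applies the same attrition, "resulting in a final 'N' of at least 400 per site".

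Item 2a gives neither alpha nor sidedness. Elsewhere in D.7.2, item 1 has a "maximum probability of type I error alpha = 5% using a one-sided" Fisher's Z test, and item 3 uses a 5% significance test. The section's opening paragraph sets the general rule that "the maximum number required to test them with sufficient power (80% or higher) will be selected".

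**The concern.** The sentence contradicts itself without any calculation. If 460 were needed in each group the total would be 920, against 500 enrolled per site; the bracket makes 460 the total. Apart from alpha, the item lists the ingredients of a standard formula, and the formula does not return 230 per group.

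This is the only sample-size calculation for the accelerometer test of Hypothesis 2, one of the four primary hypotheses, and it leads straight to the 500 per site. If its n, effect size and power cannot all hold, the protocol does not show what the enrolled sample can detect.

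**Working it through.** **Inputs.** From item 2a: two equal groups (median split), one baseline and r = 2 follow-up weights, the same correlation ρ = 0.60 between any two weights, d = 0.25 SD, 90% power (z = 1.2816). Assumed: alpha 5%, carried over from items 1 and 3, with z = 1.9600 (two-sided) or 1.6449 (one-sided). Also assumed for steps 1 to 4: d is the difference in mean follow-up weight, which is the quantity the formula compares.

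**Formula.** n per group = 2(z_α + z_β)² f / d², with f = (1 + (r − 1)ρ)/r − ρ² for the analysis of covariance.

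**1. Attempt to reproduce 230 per group.** f = 1.60/2 − 0.36 = 0.44.

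- Two-sided: 2 × 10.507 × 0.44 / 0.0625 = 147.9, so 148 per group, 296 in total.
- One-sided: 2 × 8.564 × 0.44 / 0.0625 = 120.6, so 121 per group, 242 in total.

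The plan's figure is not reproduced.

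**2. Power with 230 per group analysed.** 0.25 / √(0.88/230) = 4.042. Subtracting 1.960 leaves 2.082, or 98.1%. Subtracting 1.645 leaves 2.397, or 99.2%.

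**3. Could another correlation or analysis explain it?** With r = 2, f = 0.5 + 0.5ρ − ρ², which peaks at ρ = 0.25 with f = 0.5625. The largest possible n is then 189.1, so 190 (two-sided), or 154.1, so 155 (one-sided). No correlation gives 230 at 5%. Other analyses at ρ = 0.60, per group:

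| Analysis | f | Two-sided | One-sided |
|---|---|---|---|
| Change from baseline, two follow-ups | 0.60 | 202 | 165 |
| Follow-up mean only | 0.80 | 269 | 220 |
| Covariance, one follow-up | 0.64 | 216 | 176 |

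None gives 230.

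**4. Power at the expected retention.** 500 × 0.8 = 400, or 200 per group. 0.25 / √(0.88/200) = 3.769, which gives 96.5% two-sided or 98.3% one-sided.

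**5. Dependence on what 0.25 SD means.** Suppose it is the 24-month difference and the groups diverge linearly. The 12-month difference is then 0.125, and the mean follow-up difference is (0.125 + 0.25)/2 = 0.1875.

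- n per group: 2 × 10.507 × 0.44 / 0.03516 = about 263 two-sided, or 214.4, so 215, one-sided. Neither is 230.
- Power at 200 per group: 0.1875 / √(0.88/200) = 2.827, which gives 80.7% two-sided or 88.1% one-sided.

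**6. Can sidedness be borrowed from item 1?** Not safely. Item 1 claims 83% power for a correlation of −0.33 with 75 subjects. atanh(0.33) × √72 = 2.909, which gives 89.7% one-sided and 82.9% two-sided. The printed 83% matches the two-sided test, although the text says one-sided.

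**The case against.** The best defence is that 460 may be right under inputs the item does not print. Some combinations come close. At 0.25 SD, 95% power at two-sided 5% needs 183.0 per group, and 183.0/0.8 = 228.7, so 229 after allowing for 20% attrition. With 0.25 SD read as the 24-month difference, ρ = 0.55 and one-sided 5%, f = 0.775 − 0.3025 = 0.4725 and n = 2 × 8.564 × 0.4725 / 0.03516 = 230.2. But the first changes the stated power and counts attrition that the 500 already covers, and the second changes the stated correlation. This stands as a reason to let the authors supply their inputs, not as support for the sentence as printed.

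A reader might infer that 0.20 SD was the intended difference, because 2 × 10.507 × 0.44 / 0.04 = 231.2. The documents never mention 0.20 SD, and it is only one near-match among several.

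A reader might also see a shortfall, since 400 retained is below 460. The item uses the same verb, accrue, for both 460 and 500, so 460 reads naturally as an enrolment figure. On that reading about 460 × 0.8 = 368 are analysed, with power 95.1% two-sided or 97.6% one-sided. The 98.1% / 99.2% above apply only if all 460 are analysed.

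Three further criticisms do not hold:

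- B.9 calls the test of the study hypothesis two-sided, but explains this as either result being interpretable. It does not specify a tail and so does not contradict the one-sided tests.
- Setting a power for the D.7.1.2 method 3 slopes against the covariance power misleads, because 0.25 SD would mean a 24-month difference in one and an average in the other.
- Retitling item 2 as weight change would mislabel item 2b, which does concern body composition.

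**Conclusion.** The sentence is wrong as written on two counts. The label contradicts the split; that needs no assumption. And 460 at 90% power does not follow from the printed inputs, which give 296 (two-sided) or 242 (one-sided) in total. The second count rests on alpha of 5%, equal correlation of 0.60 and 0.25 SD as the difference in mean follow-up weight. Reading 0.25 SD as a 24-month difference with linear divergence does not rescue it: the totals are then about 526 (2 × 263) or 430 (2 × 215).

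A reader might conclude that the study is underpowered for Hypothesis 2. The documents do not support that. On either reading of 0.25 SD, the covariance analysis at 400 retained per site clears the section's 80% floor. On the 24-month reading, however, it falls short of the stated 90%, and two-sided it clears the floor only narrowly. The fault lies in what the protocol claims, not in how many it recruits.

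**What to change.** Keep 500 per site and reword item 2a:

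- Delete the words *per AEE group*.
- State the sidedness and confirm 5%; say whether n is counted at enrolment or at analysis; say whether 0.25 SD is the average follow-up difference or the 24-month difference.
- Either give the inputs that reproduce 460, or replace it. If 0.25 SD is the average follow-up difference, the totals are 296 (two-sided) or 242 (one-sided). If it is the 24-month difference with linear divergence, about 263 or 215 per group are needed for 90% power.
- State the power at 400 retained: 96.5% / 98.3% on the first reading, about 80.7% / 88.1% on the second (two-sided / one-sided).
- Say that the figure is for the baseline-adjusted covariance analysis of weight, not the unadjusted individual slopes of D.7.1.2 method 3, which the item cites.

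The cost is one paragraph, with no new participants or data. The downside is that the stated 460 and 90% change, and the power shown may be below 90% if the 24-month difference was meant.
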